5.5.1. Accelerometer Data. Each accelerometer will be initialized at the Coordinating Center (Vanderbilt) to record three-dimensional accelerations raw signal at 40 Hz. However, detailed instructions on how to wear and care for the accelerometer will be provided by the Study Coordinator at each local site during the baseline visit. Patients will be asked to wear the accelerometer secured at the right hip with a waist belt for seven consecutive days excluding night rest (sleep). All patients will also be given a stamped, self-addressed envelope to return the accelerometer to the Coordinating Center (Vanderbilt) after wearing for seven days. Research personnel at Vanderbilt will download the data using ActiLife v6.4 software. If wear interval data are not available for at least 4 days (with each day being at least 10 hours), the Research Coordinator at the Coordinating Center (Vanderbilt) will contact the patient by phone and ask them to wear the accelerometer for another 7 days. The accelerometer will then be mailed from the coordinating center (Vanderbilt) to the patient along with a self-addressed stamped envelope to return after wearing for seven days.

5.6. Phase 5: Randomization and Treatment. Once the patient has been consented, undergone surgery for a lumbar degenerative condition, and completed the baseline assessment, the Research Coordinator at each site will update the REDCap Data Management System and the patient will be randomized electronically. To ensure that the number of subjects is about the same in the two arms of the study for each clinical site, the randomization scheme will assign patients in a 1:1 ratio in randomly permuted blocks of assignments stratified by age and type of surgery (i.e.; fusion or no fusion). Block size will be determined randomly with the patient as the unit of randomization.

The randomization plan will be prepared by the study's biostatistician and administered centrally by the Coordinating Center (Vanderbilt), but will not require real time interaction with Vanderbilt staff members. Requests for randomization will be made by the study therapist using a secure web-based application. An assignment will be issued only if the database shows that the patient is eligible, the consent statement has been signed, and a baseline postoperative assessment completed. Enrollment will be documented in the patient's chart according to center protocol.

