5.6.1. Treatment. Once patients have completed the baseline assessment with the Research Coordinator and received the movement accelerometer, the study physical therapist will call the patient to schedule the first treatment session. Patients will complete 6 sessions over the phone. Sessions will be scheduled on a weekly basis.

5.7. Phase 6: Post-treatment Follow-up Phase (6 and 12 months after surgery). The randomization computer program will generate a personalized appointment schedule for the patient; this schedule will

indicate the ideal date for each follow-up visit, as well as the time window around the ideal date during which the follow-up visit may be done.

Patients will have follow-up visits at 6 and 12 months after surgery. Each visit will have an interval of time surrounding the ideal date for the visit during which the visit may be done and the data included in the trial database. The ideal date for a visit is the exact anniversary from surgery. Visit windows (+/- 2 weeks for all visits) will be constructed to be contiguous, so that at any point in time, some visit window is open, subject to a check on the minimum separation required between consecutive visits. Patients at the study follow-up visits will complete the same questions and battery of questionnaires as the baseline assessment and wear an accelerometer for 7 days. Patients will also be asked questions on intervening events such as re-hospitalization and surgery. At the 12-month follow-up, patients will return for an on-site visit and complete the performance-based tests.

Study personnel conducting the follow-up assessment will be unaware of the patient treatment condition. All data from the follow-up self-reported assessment will be entered directly into the REDCap Data Entry System by the patient or on case-report forms. Data from the performance based tests will be recorded on case report forms by study personnel and then transferred to the REDCap Data Entry System. The types of specific data to be collected at each of the follow-up visits are included as Appendix 9.4.

5.7.1. Accelerometer Data. See section 5.5.1 for procedures with regard to accelerometers.

5.8. Outcomes. All outcomes will be assessed using widely used, standardized measures. They are described below.

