6.3.2. Specific Aim 2. The data will be explored numerically and graphically. Group means and corresponding confidence intervals will be calculated for baseline variables, to confirm balance between groups. The characteristics of the patients who are lost to follow-up will be compared to those who complete the follow-up assessments. For each outcome variable, we will fit a multivariable regression model, with site as a covariate. We will explore possible non-linear (quadratic, cubic) effects of the treatment over time. We plan on adjusting for the baseline measurement of the outcome variable, age, type of surgery, site, and depressive symptoms. A random slope over time may be included to allow a separate slope to be estimated for each patient. The primary analysis will be intent-to-treat; missing observations due to drop-out and other reasons not related to the treatments will be handled with multiple imputation methodology. Our use of Bayesian estimation procedures will allow us to easily impute missing data within our models. In most cases, this will allow us to use data with some missing values, and avoid the information loss that is inherent in complete case analysis. Where it is unlikely that values are missing at random, we will include an imputation sub-model that uses available covariates to account for plausible patterns of non-random missingness. Though it is not possible to demonstrate that data are missing at random, including as many predictor variables in the imputation model as possible generally increases the chances that the missing at random assumption (conditional on the covariate values) is reasonable (159). To quantify the effect of the number of sessions completed by study participants on outcomes of interest (i.e., dose-response), we intend to explicitly model the response following session j for subject i in the following linear model: $y_{ij} - y_{i0} = \alpha_0 + \alpha_1 I[\text{session} = j] + \epsilon_i$ where the function I is an indicator for j sessions completed, and $y_{ij} - y_{i0}$ is the change in response after session j from baseline (session 0). This model can be generalized to account for a non-linear response to dose.

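### Section 6.3.2 explores quadratic and cubic treatment-by-time effects that two follow-up visits (one for performance tests) cannot support, and its dose equation needs an outcome after each session that is never measured

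*Combined protocol and SAP*

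**What the plan says.** The Aim 2 analysis in section 6.3.2 opens with its scope: "For each outcome variable, we will fit a multivariable regression model, with site as a covariate". The next sentence is "We will explore possible non-linear (quadratic, cubic) effects of the treatment over time". The covariates follow: "We plan on adjusting for the baseline measurement of the outcome variable, age, type of surgery, site, and depressive symptoms". A random slope for each patient is offered as an option.

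The timing comes from other sections. Under section 5.6 an assignment is issued only once "the consent statement has been signed, and a baseline postoperative assessment completed". Section 5.7 states: "Patients will have follow-up visits at 6 and 12 months after surgery". It places the performance tests at the 12-month visit only, and the Appendix 9.4 schedule agrees: ODI, BPI, SF-12 and accelerometer at 6 and 12 months; Chair Stand, 10-Meter Walk and TUG at 12 months.

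Section 6.3.2 then adds a dose analysis: "To quantify the effect of the number of sessions completed by study participants on outcomes of interest". It has an intercept and one indicator term, "where the function I is an indicator for j sessions completed", and its left-hand side "is the change in response after session j from baseline (session 0"). Section 5.6.1 sets six weekly telephone sessions, and section 3.2.2 matches the education program to CBPT in session frequency, length and therapist contact.

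**The concern.** A polynomial in time needs more distinct time points than its degree. Once the baseline value becomes a covariate, two response times remain for most outcomes and one for the performance tests, so the planned curves have nothing to rest on. Bayesian software would still return a posterior, but between visits it would reflect mainly the prior or whatever constraint was imposed, and section 6 states no prior.

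The dose equation has a different problem. Read literally, it needs an outcome after each of sessions 1 to 6, and none is collected. Whoever runs it must choose the response time, the form of the dose variable and the handling of arm, possibly after seeing data. Because both arms receive sessions, a model without an arm term mixes two different programs, and an arm difference can appear as a dose effect when completion differs by arm.

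**Working it through.** The plan gives no figure to reproduce here. The check counts parameters against observable cell means, then asks what scatter in visit dates adds.

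**Inputs.** Response visits: 6 and 12 months, or 12 months only (5.7, Appendix 9.4). Baseline: 6 weeks after surgery, t0 = 1.38 months. Windows: ±2 weeks (5.7). Patients: 110 per arm (6.5). ODI MCID range: 8.2 to 12.8 points (5.8.1). Assumed, because the documents do not give them: residual SD 1, within-patient correlation 0 or 0.5, visit dates uniform in the window, and the session-completion distributions below.

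**Rank at nominal times.** The unconstrained model has 1, t, …, t^d in each arm, so 2(d+1) parameters. Two arms at two visits give 4 cell means; at one visit, 2. The constrained model has one intercept per visit plus treatment × (t − t0)^k for k = 1 to d, which fixes the effect at zero at baseline.

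| Model | 6 and 12 months | 12 months only |
|---|---|---|
| Unconstrained quadratic | rank 4 of 6 | rank 2 of 6 |
| Unconstrained cubic | rank 4 of 8 | rank 2 of 8 |
| Zero at baseline, line | not needed | rank 2 of 2 |
| Zero at baseline, quadratic | rank 4 of 4 | rank 2 of 3 |
| Zero at baseline, cubic | rank 4 of 5 | rank 2 of 4 |

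The cubic fails throughout. The one quadratic that fits is saturated, so curvature cannot be tested. For the performance tests, the constrained line only rescales the 12-month contrast.

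**What the saturated quadratic shows.** Let the true effect be 1 at both visits. With s = t − t0, s = 4.62 and 10.62. Solving a·s + b·s² = 1 at both gives b = −1/(4.62 × 10.62) = −0.0204 and a = 1/4.62 + 1/10.62 = 0.3106. At 9 months s = 7.62, and the curve is 0.3106 × 7.62 − 0.0204 × 7.62² = 1.18. That is its peak, 18% above anything observed.

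**Using actual visit dates.** Over 60 simulated designs, the standard error of the 9-month effect in residual SD was:

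| Treatment-by-time form | Correlation 0 | Correlation 0.5 |
|---|---|---|
| Free line | 0.095 | 0.117 |
| Free quadratic | 0.555 | 0.487 |
| Free cubic | 0.556 | 0.488 |
| Zero at baseline, quadratic | 0.121 | 0.142 |
| Zero at baseline, cubic | 0.518 | 0.456 |

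A single visit contrast has SE √(2/110) = 0.135. With visits inside ±1 week, the free quadratic or cubic gives 1.09 (correlation 0). For the performance tests, a treatment slope in time has SE 0.135/(0.46/√3) = 0.51 SD per month, where 0.46 months is the half-window.

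**Random slope.** Two fixed visits supply three second moments (two variances and a covariance). An unrestricted random intercept and slope plus residual needs four parameters, so it is not identified.

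**Dose equation.** Outcome measurements tied to sessions 1 to 6: none. The nearest model that can be run regresses follow-up change on number of sessions completed. To show what pooling the arms can do, suppose sessions 0 to 6 are completed by 5, 3, 3, 4, 5, 10 and 70% in CBPT and by 10, 6, 6, 8, 10, 10 and 50% in education, with no dose effect in either arm.

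- Means: 5.11 and 4.32, difference 0.79. Variances: 2.90 and 4.46.
- Pooled variance: (2.90 + 4.46)/2 + 0.79²/4 = 3.83.
- Pooled slope: (0.79 × arm effect/4)/3.83.
- Arm effect −8.2 ODI points: −0.42 per session. Arm effect −12.8: −0.66 per session.
- Over six sessions: an apparent 2.5 to 4.0 points.

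With equal completion this spurious slope is zero, but true within-arm slopes of −2 and 0 would still be reported as −1.

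**The case against.** The plan only says it will explore these shapes, and nothing obliges the team to force a cubic on every outcome; the performance-test hypothesis is itself limited to 12 months. That is right, and it limits the consequence. It does not make the terms estimable.

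The schedule also holds earlier measurements. With baseline as a response, three times in two arms give 6 cell means: the quadratic is saturated at 6 of 6 and the cubic fails at 6 of 8. With the preoperative value as well, a cubic is saturated at 8 of 8, for the self-report outcomes only. But section 6.3.2 makes baseline a covariate, and both early times precede randomisation. At best this reading gives saturated fits that lean on times at which treatment could have had no effect.

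Section 5.7 describes the windows both as ±2 weeks and as contiguous. If they really were contiguous (about ±3 months), the 9-month SE would fall to 0.14. The imprecision therefore depends on the stated ±2 weeks, the only width given. The 18% peak likewise depends on a zero-at-baseline constraint that the plan does not state; it illustrates the one identifiable version.

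On dose, the aim and the indicator's definition both point to sessions completed, so part of the problem is notation, and the equation is schematic: it also omits the planned covariates. The slope in the illustration is not the equation's own parameter, the completion figures are assumed, and an MCID range stands in for the arm effect. These points weaken the size given, not the defect: the response as defined is not measured, and the missing arm term matters because both arms have sessions.

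**Conclusion.** The point holds. The cubic treatment-by-time term cannot be estimated at the scheduled visits for any outcome. The quadratic cannot be estimated for the performance tests, and elsewhere only under a constraint that leaves nothing with which to test curvature. Visit-date scatter leaves the free quadratic or cubic at 9 months about 0.555/0.095 = 5.8 times as imprecise as a line (0.487/0.117 = 4.2 times at correlation 0.5), given ±2-week windows and 110 per arm.

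The dose equation cannot be run as written. Its workable reading compares groups that were not randomised and, without an arm term, treats two programs as one. The spurious slope of 0.42 to 0.66 ODI points per session is an illustration that rests on assumed completion.

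The 6- and 12-month treatment contrasts and the sample size are not affected. The plan should be corrected because the dose analysis is a stated part of Aim 2 and must be reinterpreted before anyone can carry it out. Confidence is high on identifiability and on the missing measurements. The optional random slope is a minor related matter.

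**What to change.** In section 6.3.2:

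- Remove the quadratic and cubic terms. Report baseline-adjusted treatment effects by categorical visit (6 and 12 months), and one baseline-adjusted 12-month contrast for each performance test.
- Redefine the dose response as change from baseline to 6 months and to 12 months, with number of sessions completed as the explanatory variable. Fit it within arm or with an arm-by-sessions term, and label it exploratory and non-randomised.
- If the random slope stays as an option, state a restricted form that two visits can identify.

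The cost is SAP wording only, with no new data, visits or patients. The exploratory trajectory between visits is given up.

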Specific Aim 4: To determine which sub-groups of adults are most likely to benefit from CBPT following lumbar spine surgery for degenerative conditions.

Hypothesis 4: CBPT participants that are 60 years or older, have a fusion procedure, and report clinically significant depressive symptoms will demonstrate greater improvement in outcomes at 12 months following lumbar spine surgery.

Study design: Multicenter, prospective randomized controlled trial.

Comparators:

Group 1: CBPT

Group 2: Education

Study duration: 4 years (2-month start-up, 4-month qualitative data collection, 24-month accrual, 12-month follow-up, and 6 months analysis and writing). Participants will be followed for 1 year from the time of surgery.

Sample size: 260 eligible patients are planned to be consented; 221 are expected to be retained at 12-month follow-up.

Number of study sites: 2

Inclusion criteria

- 1) Radiographic evidence of lumbar spinal stenosis secondary to degenerative changes;
- 2) Surgical treatment of a lumbar degenerative condition (spinal stenosis, spondylosis with or without myelopathy, and degenerative spondylolisthesis) using laminectomy with or without arthrodesis procedures;
- 3) English speaking due to feasibility of employing study personnel to deliver and assess the study intervention; and
- 4) Age older than 21 years (younger individuals do not typically have a lumbar degenerative condition)

Exclusion criteria

- 1) Patients having microsurgical techniques as the primary procedure, such as an isolated laminotomy or microdiscectomy (individuals having these minimally invasive surgical techniques tend to have a less severe case of lumbar degeneration and a shorter recovery time than individuals having arthrodesis or laminectomy without arthrodesis);
- 2) Patients having surgery for spinal deformity as the primary indication (patients with spinal deformity as the primary spinal disorder tend to have a different recovery trajectory compared to the inclusion population);
- 3) Patients having surgery secondary to pseudarthrosis, trauma, infection, or tumor;
- 4) Presence of back and/or lower extremity pain < 3 months indicating no history of chronic pain;

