Huntington's disease, Alzheimer's disease, Muscular Dystrophy, Stroke, Autonomic Nervous System disorders, Traumatic Brain Injury, Cerebral Palsy, and Amyotrophic Lateral Sclerosis;

6) Presence of schizophrenia or other psychotic disorder, including but not limited to Brief Psychotic disorder and Delusional disorder;

7) Patients not able to return to clinic for standard follow-up visits with surgeon due to time and travel limitation;

8) Patients having surgery under a workman's compensation claim; and

9) Unable to provide a stable address and access to a telephone indicating the inability to participate in either the telephone-based CBPT or education program.

5. Trial Protocol

5.1. Overview. The patient-related activities of the CBPT trial can be divided into the following phases:

- Phase 1: Qualitative data collection (Vanderbilt site only)
- Phase 2: Screening for eligibility;
- Phase 3: Consent and enrollment into trial prior to surgery;
- Phase 4: Baseline data collection (6 weeks after surgery);
- Phase 5: Randomization and Treatment;
- Phase 6: Post-treatment follow-up phase (6 and 12 months after surgery);

The visit and data collection schedule described below is summarized in Appendix 9.4.

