5.2.3. Pilot Testing and Cognitive Interviews. The final outcome measures/items will be piloted via mail or email with 25 patients who have participated in the interviews or focus groups. Ten additional patients will be recruited for in-person cognitive interviews (i.e., talk out loud as they complete the measurement tool). The cognitive interviews will assess the following for the outcome scales/items: 1) comprehension; 2) process by which the respondent retrieves relevant information from memory; 3) decision process to answer each item; and 4) response process.

5.3. Phase 2: Screening for Eligibility. Patients will be screened for eligibility in each center by the local research coordinator in close coordination with the surgeon co-investigators. Screening through the medical record will occur prior to surgery and a scheduled preoperative clinic visit. Additional screening will occur either during the preoperative clinic visit or after by the study coordinator through a list of screening questions. All potentially eligible patients will be entered into REDCap, a study number assigned, and eligibility criteria confirmed. The Coordinating Center (Vanderbilt) will be available to adjudicate eligibility.

5.4. Phase 3: Consent and Enrollment. Eligibility will be confirmed with the treating surgeon and through a list of screening questions for the patient. Patients will then be approached for their consent to participate in the randomized controlled trial following their preoperative clinic visit. The study coordinator will perform the consent process using a scripted dialogue and materials developed for the CBPT study. A power point presentation will also be made available for use by the research team to describe the study and what it means to participate in the study.

Once consented into the randomized trial, patients will complete a preoperative questionnaire. This assessment will gather data on patient demographic and injury characteristics, medical and social history, expectations of surgery, fear of movement, pain self-efficacy, affect, depressive symptoms, and preoperative levels of pain, disability, and general physical and mental health. Patients will also be asked to complete a battery of physical performance tests to assess strength, mobility, and gait speed.

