9.4. Data Collection Schedule

Assessment/Procedure	Pre-op	Baseline	6 month	12 month
Patient Consent	X			
Patient Characteristics				
Age, Gender, Race/Ethnicity	X			
Marital Status	X			
Educational Level	X			
Insurance Status	X			
Height/Weight	X			
Smoking Status	X	X	X	X
Working status	X	X	X	X
Medical History/Co-morbidities				
Pain Duration	X			
Prior Spinal Surgery	X			
Co-morbidities	X	X	X	X
Current medications	X	X	X	X
Intervening Events		X	X	X
Surgical Characteristics				
Type (fusion/no fusion)	X			
Spinal levels	X			
Revision (yes/no)	X			
Psychosocial Characteristics				
Fear of Movement (TSK)	X	X	X	X
Pain Self-Efficacy (PSEQ)	X	X	X	X
Depressive Symptoms (PHQ-9)	X	X	X	X
Expectations of Recovery	X			
Satisfaction		X	X	X
Primary and Secondary Outcomes				
Pain (BPI)	X	X	X	X
Disability (ODI)	X	X	X	X
General Health (SF-12)	X	X	X	X
Chair Stand	X	X		X
10 Meter Walk	X	X		X
Functional Mobility (TUG)	X	X		X
Physical Activity Counts (Accelerometer)		X	X	X
Health Services Utilization				
Physical Therapy Services	X	X	X	X
Narcotic Use	X	X	X	X
Re-hospitalization		X	X	X
Additional Surgery		X	X	X

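### The Aim 2 model could also adjust for the preoperative score of the outcome, which is already scheduled for collection: an optional gain in precision, not an error

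*Combined protocol and SAP*

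**What the plan says.** - **Covariates.** Section 6.3.2 applies one covariate list to each outcome: "We plan on adjusting for the baseline measurement of the outcome variable, age, type of surgery, site, and depressive symptoms". The baseline value is the only earlier score of the outcome in that list.
- **Meaning of baseline.** Section 5.1 has "Phase 4: Baseline data collection (6 weeks after surgery" as a step of its own, after consent and before randomization. Section 5.5 describes the same visit.
- **Preoperative scores.** Section 5.4 states: "Once consented into the randomized trial, patients will complete a preoperative questionnaire". It covers, among other things, "preoperative levels of pain, disability, and general physical and mental health", and patients are also asked to do the performance tests. Appendix 9.4 agrees. The BPI, ODI and SF-12 are marked at the preoperative, baseline, 6-month and 12-month points. The chair stand, 10-meter walk and Timed Up and Go are marked preoperatively, at baseline and at 12 months.
- **Exception.** The row "Physical Activity Counts (Accelerometer" in Appendix 9.4 has no preoperative mark.
- **Condition for randomization.** Section 5.6 issues an assignment once the database shows eligibility and that "the consent statement has been signed, and a baseline postoperative assessment completed". A completed preoperative questionnaire is not named.
- **Imputation.** Sections 6.3.2 and 6.4 favour a wide set of predictors in the imputation model but do not name the preoperative scores.

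**The concern.** Randomization follows the 6-week visit, so a preoperative score cannot be affected by treatment and is a legitimate covariate. The 6-week score is taken during early surgical recovery, and a score from before surgery may carry separate information about where the patient will stand at 12 months. If it does, leaving it out makes the interval for the treatment effect wider than it need be, on outcomes that include all the primary ones, when the schedule already asks patients for the measurement. Only precision is at stake, not validity. The covariate has to be named in advance, because one added after the results are known invites criticism.

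**Working it through.** **The plan's own figures.** The Design Synopsis gives "260 eligible patients are planned to be consented; 221 are expected to be retained at 12-month follow-up". 221/260 = 0.850, an implied loss of 15%. Section 6.5 targets 110 per arm, or 220 in all; 220/0.85 = 258.8, rounded up to 259, and 221/0.85 = 260. These figures agree with one another. Power cannot be reproduced, because no effect size, SD or power result is stated. The power model in 6.5 regresses change from baseline on treatment alone, so it counts on no gain from covariates.

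**Inputs for the gain.** The documents give no correlation between visits, so these ranges are assumptions:
- r1, 6-week with 12-month score: 0.4 to 0.6
- r2, preoperative with 12-month score: 0.3 to 0.5
- r12, preoperative with 6-week score: 0.3 to 0.5

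**Formulas**, with the outcome variance set to 1:
- Residual variance with the 6-week score alone: V1 = 1 − r1².
- With both scores: V2 = 1 − (r1² + r2² − 2·r1·r2·r12)/(1 − r12²).
- Fall in variance = 1 − V2/V1, which is the squared partial correlation of preoperative with 12-month score given the 6-week score.
- Equivalent increase in sample = V1/V2 − 1.

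**Results within the assumed ranges**

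| Case (r1/r2/r12) | V1 | V2 | Fall in variance | Equivalent sample increase |
|---|---|---|---|---|
| Lowest, 0.6/0.3/0.5 | 0.640 | 1 − 0.27/0.75 = 0.640 | 0% | 0% |
| Central, 0.5/0.4/0.4 | 0.750 | 1 − 0.25/0.84 = 0.702 | 6.3% | 6.8% (220 × 0.068 ≈ 15) |
| Highest, 0.4/0.5/0.3 | 0.840 | 1 − 0.29/0.91 = 0.681 | 18.9% | 23.3% (220 × 0.233 ≈ 51) |

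The lowest case is exactly nil because the numerator of the partial correlation is 0.3 − 0.6 × 0.5 = 0. In the central case the standard error falls by about 3% (√(0.702/0.750) = 0.968), and a power of 80% would become about 82.5%.

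**Sensitivity to the correlation pattern.** If all three correlations are equal, the fall runs from 5% (at 0.3) to 17% (at 0.7). If correlation weakens with time, it is about 2% (0.5/0.3/0.4 or 0.6/0.4/0.5). Under first-order decay (0.5/0.25/0.5) it is nil.

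**Cost of the extra covariate.** At n = 220, going from 7 to 8 coefficients inflates the expected variance by about (220 − 7 − 2)/(220 − 8 − 2) = 211/210 = 1.005, or 0.5%. The break-even partial correlation is √(1 − 210/211) ≈ 0.07.

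**What the plan already gains.** With equal variances at the two visits, a change score has variance 2(1 − r1), against 1 − r1² when the 6-week score is a covariate. The ratio is (1 + r1)/2, so for r1 from 0.3 to 0.7 the planned adjustment already removes 35% to 15% of the variance in the model used for power.

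**The case against.** The strongest reply is that the plan is sound as it stands. It adjusts for the last score before treatment, the two stratification factors, site and depressive symptoms. The estimate is unbiased, and the sample size rests on a model with no covariates. A second earlier score is a refinement. All of this stands.

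The gain is also unproven. Surgery falls between the preoperative and 6-week measurements, so the preoperative score may add little once the 6-week score is known. The calculation leaves out the other covariates, and depressive symptoms in particular may carry part of the same information. A reader might infer that precision is certainly being given up; the documents do not support that, because they give no correlations and plausible values include no gain at all.

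Three other strong readings also fail:
- *That the 6-week score is the only adjustment.* It is the only earlier score of the outcome, but four other covariates are listed.
- *That the preoperative score will be available for every consented patient.* It is scheduled, but completing it is not a condition of randomization.
- *That the change is free.* If the partial correlation is below about 0.07, precision is slightly lost.

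On imputation, the plan's preference for many predictors already leaves room for the preoperative scores. Not naming them is a missing detail, not a gap in the method. Finally, the change ends the single covariate set for all outcomes, because the accelerometer measure has no preoperative value.

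None of this argues against the suggestion: the likely cost is about half a percent of variance, against a central assumed gain of about 6%.

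**Conclusion.** The point holds as an optional improvement in efficiency. The preoperative score of the ODI, BPI, SF-12 PCS and MCS and the three performance tests is a valid pre-randomization covariate that is already scheduled, and 6.3.2 does not use it. It would be wrong to infer that the planned analysis is biased or that the trial is underpowered for this reason. The size of the gain rests wholly on assumed correlations, which are set out above with their results, and it may be smaller with the other covariates in the model. Confidence is high that the score is scheduled and unlisted, and low on how much it would bring.

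**What to change.** In 6.3.2, add to the covariate list, for the ODI, BPI, PCS, MCS, chair stand, 10-meter walk and Timed Up and Go: *and the preoperative value of the same outcome, where collected*. State that missing preoperative values are imputed under the planned procedure, and that the accelerometer model keeps its present covariates. Fix this before outcome data by arm are seen. If the pilot data used for the power simulation in 6.5 include preoperative scores, which the documents do not say, check the partial correlation there first; a value near or below 0.07 would be a reason to leave the plan alone.

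Cost: one phrase, no new data collection, one degree of freedom per outcome, some missing preoperative values to impute, and a covariate set that differs for the accelerometer outcome.
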